2.2.2 Secondary Endpoints (or Secondary Evaluation Metrics) and Definitions

1. Hamilton Anxiety Rating Scale (HAMA) score during follow-up: The total score effectively reflects the severity of anxiety symptoms and can be used to evaluate the severity of anxiety in patients with anxiety and depressive disorders and to assess the effects of various drug and psychological interventions.

According to data from the Chinese Scale Collaboration Group: Total score ≥ 29 : Possible severe anxiety; Total score ≥ 21 : Definite significant anxiety; Total score ≥ 14 : Definite anxiety; Total score > 7 : Possible anxiety; Total score ≤ 7 : No anxiety symptoms.

2. HAMD response rate: Reduction in HAMD-17 score $\geq 50\%$.

3. HAMD remission rate: Post-treatment HAMD-17 score ≤ 7 .

4. Beck Depression Inventory (BDI) score: A tool specifically designed to assess depression severity. The entire questionnaire comprises 21 groups of items, each with 4 statements preceded by corresponding numbers as grade scores.

Scoring criteria: 0-4: (Essentially) no depressive symptoms; 5-7: Mild depression; 8-15: Moderate depression; ≥ 16 : Severe depression.

5. Generalized Anxiety Disorder 7-item (GAD-7) score: The GAD-7 consists of 7 items aiming to understand how often the respondent has been bothered by 7 problems including feeling nervous or anxious over the past 2 weeks.

Scoring rules: Each item scores 0-3, total score 21. 0-4: No generalized anxiety; 5-9: Mild generalized anxiety; 10-14: Moderate generalized anxiety; 15-21: Severe generalized anxiety

6. PTSD Checklist-Civilian Version (PCL-C) score: Developed in 1994 by the Behavioral Science Division of the US National Center for PTSD, translated into Chinese by Professors Jiang Chao and Zhang Jie in 2003. The scale includes 17 items categorized into 3 characteristic symptom clusters: re-experiencing (5 items), avoidance (7 items), and hyperarousal (5 items). Each item uses a Likert 5-point scale from 1 (not at all) to 5 (extremely). Total score range 17-85, with higher scores indicating a higher likelihood of PTSD.

Test results: 17-37: No significant PTSD symptoms; 38-49: Some degree of PTSD symptoms; 50-85: Significant PTSD symptoms, possible PTSD diagnosis

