5.1 Randomization

5.1.1 Method for Generating Random Allocation Sequence

Stratified block randomization will be used: Eligible patients will be randomly assigned to Group A or B in a 1:1 ratio. Using R software, stratification will be based on age (two levels: 18-60 years, >60 years) and gender (two levels: male, female), resulting in 4 strata. Within each stratum, patients will undergo randomization with varying block sizes. The output will determine the stimulation device assigned to each patient.

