9.1 Sample Size Determination

This is a randomized controlled trial. Significance level (α) is set at 0.05, and power ($1-\beta$) at 0.80. Based on literature, the effect size for taVNS alleviating depression is approximately 57%. Using PASS software, the calculated sample size per group is $n_1=n_2=56$. Considering a 10% dropout/loss-to-follow-up rate and the need for stratification by age and gender, the minimum sample size per group is determined to be 60, resulting in a total sample size of 120.

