9.3.2 Analysis of Secondary Endpoints

Comparisons of HAMA scores, BDI scores, GAD-7 scores, PCL-C scores, SF-36 scores, HRV parameters, echocardiography parameters, and blood biomarkers between groups will be performed using t-tests or non-parametric tests. Comparison of HAMA response rates, remission rates, and MACE incidence between groups will be performed using chi-square tests.

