9.4 Safety Analysis and Statistical Methods

Statistical analysis will be performed using SPSS 26.0 software. Categorical data will be presented as counts and percentages. Normally distributed continuous data will be presented as mean \pm standard deviation; non-normally distributed continuous data will be presented as median and interquartile range. Differences between groups for normally distributed continuous data and categorical data will be compared using independent samples t-tests and chi-square tests, respectively. Non-parametric tests will be used for non-normally distributed continuous data. Bayesian analysis will be employed to further explore the impact of different stimulation modalities on outcome prognosis. All statistical tests will be two-sided, with a P-value <0.05 considered statistically significant.

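### The unadjusted chi-square for HAMD remission ignores baseline HAMD, which gives up some power and lets a chance baseline imbalance shift the remission difference

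*Protocol*

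**What the plan says.** Protocol section 9.3.2 names the test for the binary secondary endpoints: "Comparison of HAMA response rates, remission rates, and MACE incidence between groups will be performed using chi-square tests". Section 9.4 repeats the chi-square as the general rule for categorical data. No section of the protocol adjusts for baseline.

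Section 2.2.2 defines response as a fall of at least 50% in HAMD-17, and remission as an absolute level: "HAMD remission rate: Post-treatment HAMD-17 score ≤ 7". Section 7.1 lists HAMD response and HAMD remission for efficacy. No HAMA response or remission endpoint is defined anywhere, so the sentence in 9.3.2 is read here as meaning HAMD.

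Section 4.1 admits HAMD-17 scores from 7 up to but not including 24. In section 5.1.1, "stratification will be based on age (two levels: 18-60 years, >60 years) and gender (two levels: male, female), resulting in 4 strata"; baseline HAMD is not a factor. It is recorded in the baseline table of section 10.1.

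**The concern.** Under a fixed cut-off of 7, a patient who enters at 8 needs a 1-point fall to remit and one who enters at 23 needs a 16-point fall. A patient who enters at 7 already meets the cut-off. Entry severity therefore predicts remission by construction, whatever the treatment does.

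Nothing in the randomization balances entry severity, and the stated test cannot account for it. Two things are at stake for remission: power that the same data could supply, and exposure of the observed difference to a chance imbalance in baseline HAMD. Adjusting the primary score in 9.3.1 would not touch this sentence, so it needs its own edit.

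**Working it through.** **Inputs from the protocol.** Two-sided 5% tests and 80% power (9.1, 9.4). 1:1 allocation (5.1.1). 56 per group before dropout, then "the minimum sample size per group is determined to be 60, resulting in a total sample size of 120" (9.1). Entry HAMD 7 to 23 (4.1). Remission at 7 or less (2.2.2). Section 9.1 also says "the effect size for taVNS alleviating depression is approximately 57" per cent. This is read here as d = 0.57; a 57% response rate is the other possible reading.

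**Assumed, because the protocol gives no values.** Baseline distribution, Week 8 SD, improvement on sham, and the correlation between baseline and Week 8 HAMD.

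**Step 1: the plan's own figure.** With d = 0.57, n = 2 × (1.960 + 0.842)² / 0.57² = 48.3, so 49 per arm (50 by the exact t-test). The stated 56 appears if the 10% dropout is already included (50 / 0.9 = 55.6), if power is 0.85, or if 57% is a response rate against an unstated control rate near 31%. The present point does not rest on that figure. No power is stated for remission or response.

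**Step 2: how far remission depends on baseline.** Take baseline uniform on 7 to 23 (mean 15, SD √[(17² − 1)/12] = 4.90), a 30% mean fall on sham (Week 8 mean 10.5), Week 8 SD 4.5 and correlation 0.5. The slope is 0.5 × 4.5 / 4.90 = 0.459 and the residual SD is 4.5 × √0.75 = 3.90. Scores are whole numbers, so the cut is at 7.5.
- Sham patient entering at 8: expected Week 8 score 10.5 − 0.459 × 7 = 7.29; remission probability Φ[(7.5 − 7.29)/3.90] = 52%.
- Sham patient entering at 23: expected score 10.5 + 0.459 × 8 = 14.17; probability Φ[(7.5 − 14.17)/3.90] = 4%.

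**Step 3: power of the planned test.** Under the same values, sham remission is Φ[(7.5 − 10.5)/4.5] = 25%. The active mean is 10.5 − 0.57 × 4.5 = 7.94, giving 46%. With 56 per arm the normal approximation gives (0.209 − 1.96 × 0.0905)/0.0884 = 0.36, so power is about 64%.

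**Step 4: gain from adjustment, by simulation.** Pearson chi-square against a likelihood-ratio test for arm in a logistic model with baseline HAMD.

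| Setting | Correlation | Remission power, chi-square | Remission power, adjusted |
|---|---|---|---|
| 56 per arm, uniform baseline, Week 8 SD 4.5 | 0.3 | 63.9% | 66.1% |
| | 0.5 | 64.4% | 72.0% |
| | 0.7 | 60.6% | 80.1% |
| 54 per arm (60 × 0.9), baseline mean 15 and SD 4 truncated to 7–23, Week 8 SD 5, effect 0.57 × 5 = 2.85 points | 0.3 | 63% | 67% |
| | 0.5 | 64% | 73% |
| | 0.6 | 62% | 75–76% |

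At zero correlation the adjusted test still appeared to gain about 1.6 points, so part of the gain at 0.3 is small-sample test size and not precision. If patients instead fall by a percentage of their baseline, the remission gain runs from 1 to 17 points.

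For response, the gain was 0 to 2 points in most settings of the first type (at most 6), and about 1 to 3 in the second. The correlation of response with baseline ran from about +0.2 to −0.35 as the assumptions changed, and was about 0 under proportional improvement.

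**Step 5: chance imbalance, no treatment effect.** One standard error of the baseline difference is 4.90 × √(2/56) = 0.93 HAMD points. The shift per HAMD point is corr(remission, baseline) × SD(remission) / SD(baseline). At correlation 0.5 this is 0.37 × √(0.25 × 0.75) / 4.90 = 3.3 percentage points.

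| Correlation | Shift in remission difference per HAMD point | Rejection rate at a 2-SE imbalance | Rejection rate overall |
|---|---|---|---|
| 0.3 | 2.0 points | 7% | 5% |
| 0.5 | 3.3 points | 10% | 5% |
| 0.7 | 4.8 points | 13% | 5% |

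The arm with the lower baseline gains. For response the shift was +1.7, +0.3 and −1.2 points, and the rejection rate at 2 SE stayed between 4% and 6%.

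**The case against.** The strongest reply is that the plan is not wrong. Randomization makes the chi-square valid, and its overall error rate is 5% in every setting. A reader might infer from the last table that the false-positive rate is inflated. It is not: the higher rates apply only given an unusual imbalance, and they average out over randomizations.

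A reader might also extend the point to both binary endpoints. That does not hold in general. Response is already scaled to each patient's own baseline, and its remaining dependence is weak and of uncertain sign.

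Three further replies stand in part.
- The size of the gain rests on values that the protocol does not give. This is true, and the range is wide.
- The replacement has its own small-sample cost. Tested by a delta-method interval for the marginal risk difference, null rejection for remission was 5.9% to 6.6%, against 5.0% to 5.8% for the chi-square. The four-term logistic model gave 4.8% to 6.2%. The variance estimator therefore needs care.
- These are secondary endpoints for which no power is promised, and an effect estimate with an interval may be left to the statistical analysis plan. The absence of an interval is accordingly not counted as a fault. The test itself is written into 9.3.2 and can be judged as it stands.

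Adjustment would not settle how patients who enter at 7, already within the remission range, are to be counted. That is a separate question of definition.

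**Conclusion.** The point holds for remission, as a matter of efficiency and precision. By its definition and the entry range, remission depends on a collected variable that the stated analysis ignores. With 54 to 56 per arm, Week 8 SD 4.5 to 5 and d = 0.57, adjustment is worth about 2 to 4 points of power at correlation 0.3 (partly test size), about 8 to 9 at 0.5 and more above that. A baseline imbalance moves the unadjusted difference by about 2 to 5 percentage points per HAMD point at correlations 0.3 to 0.7.

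The documents do not support calling the chi-square invalid or claiming a material loss for response. The HAMA/HAMD mismatch in the same sentence is a plain wording error and does not depend on any assumption.

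**What to change.** In section 9.3.2:
1. Correct HAMA to HAMD for the response and remission rates.
2. Compare HAMD remission at Week 8 (the end of treatment) by logistic regression on arm, baseline HAMD, age group and gender. Treat response the same way for consistency.
3. Report the standardized (marginal) risk difference with a 95% CI, from a bootstrap or a variance estimator adequate for arms of this size.
4. Keep the chi-square as a supportive analysis. The MACE comparison is not affected.

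The change needs no added patients, visits or measurements, since all covariates are already collected. The cost is slightly more analysis work. Standardization may also need software other than SPSS 26.0, which section 9.4 names; R is already used for the randomization.

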9.4 Safety Analysis and Statistical Methods

Statistical analysis will be performed using SPSS 26.0 software. Categorical data will be presented as counts and percentages. Normally distributed continuous data will be presented as mean \pm standard deviation; non-normally distributed continuous data will be presented as median and interquartile range. Differences between groups for normally distributed continuous data and categorical data will be compared using independent samples t-tests and chi-square tests, respectively. Non-parametric tests will be used for non-normally distributed continuous data. Bayesian analysis will be employed to further explore the impact of different stimulation modalities on outcome prognosis. All statistical tests will be two-sided, with a P-value <0.05 considered statistically significant.

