9.6 Data Monitoring Committee

Given the low incidence and mild nature of adverse reactions associated with this trial, and its high safety profile, a Data Monitoring Committee will not be established.

10. Data Collection and Management

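### Section 9.4 fixes P<0.05 tests as the only stated between-group safety comparison, with no between-group estimate or interval, in a trial of 60 per arm sized only for depression

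*Protocol*

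**What the plan says.** Protocol 9.4 carries the safety analysis. For description it says "Categorical data will be presented as counts and percentages", with mean and SD or median and IQR for continuous data. For comparing the arms it says "Differences between groups for normally distributed continuous data and categorical data will be compared using independent samples t-tests and chi-square tests, respectively", with non-parametric tests for non-normal data. The decision rule is "All statistical tests will be two-sided, with a P-value <0.05 considered statistically significant". One further sentence reads "Bayesian analysis will be employed to further explore the impact of different stimulation modalities on outcome prognosis"; it names no safety variable, prior or threshold. No risk difference, risk ratio, mean difference, confidence interval or upper bound appears.

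MACE is handled separately, in 9.3.2, again by a test alone: "Comparison of HAMA response rates, remission rates, and MACE incidence between groups will be performed using chi-square tests".

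The sample size in 9.1 rests on the effect on depression, and "the minimum sample size per group is determined to be 60, resulting in a total sample size of 120". Section 9.6 explains the absence of a monitoring committee thus: "Given the low incidence and mild nature of adverse reactions associated with this trial, and its high safety profile". It gives no rate.

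**The concern.** A significance test asks whether the data are surprising if the arms do not differ. For harm, a reader mainly needs to know how large an excess risk remains compatible with the data. In a small trial with infrequent events, a P-value above 0.05 says almost nothing on that question, because both a harmless device and one that doubles the risk will usually give that result.

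This matters here for three reasons. The trial was sized for depression, so nothing ensures that the safety comparison is informative. The protocol itself calls adverse reactions infrequent, and that is where a chi-square test on 60 per arm is weakest. With no interim analysis (9.5) and no monitoring committee (9.6), the final comparison is the only planned statistical look at harm between arms, in a population for which the Introduction says taVNS research is limited.

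**Working it through.** **Inputs from the protocol.** 60 per arm (9.1), 1:1 allocation (5.1.1), 10% loss (9.1), two-sided 5% level and chi-square or t-test (9.4). After loss, 60 × 0.9 = 54 per arm.

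**Inputs assumed.** The protocol states no AE rate, safety power or safety margin, so there is no safety figure of its own to reproduce. Sham risks of 1% to 10% are assumed below. The calculation uses only 60 or 54 per arm and does not depend on how the efficacy figure in 9.1 was derived.

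**Step 1: approximate power of the chi-square test.** With p̄ the mean of the two risks,

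power ≈ Φ{ [ |p₁−p₂|·√n − 1.96·√(2p̄(1−p̄)) ] / √(p₁(1−p₁)+p₂(1−p₂)) }

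- 5% vs 10%, n = 60: (0.387 − 0.730)/0.371 = −0.92, so power is 18%.
- 10% vs 20%, n = 60: (0.775 − 0.990)/0.500 = −0.43, so power is 33%.

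**Step 2: exact miss rates.** All 2×2 tables were enumerated with their binomial probabilities, rejecting when the uncorrected Pearson chi-square exceeds 3.84. The miss rate is the probability of not rejecting.

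| Sham vs active (assumed) | Missed, 60 per arm | Missed, 54 per arm |
|---|---|---|
| 1% vs 2% | 98% | 99% |
| 2% vs 4% | 93% | 94% |
| 5% vs 10% | 83% | 84% |
| 10% vs 20% | 67% | 70% |
| 2% vs 8% | 69% | 72% |
| 5% vs 15% | 54% | 58% |
| 10% vs 30% | 20% | 24% |
| 5% vs 25% | 10% | 13% |

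By the formula in step 1, 80% power at 60 per arm needs an active risk of 16.8%, 22.4% or 30.3% against a sham risk of 2%, 5% or 10%.

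**Step 3: continuous safety measures.** For a 0.5-SD shift, the noncentral t distribution gives a miss rate of 22% at 60 per arm and 27% at 54. The weakness is therefore mainly in the event data.

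**Step 4: what an interval would add.** Take illustrative counts of 8/60 active and 3/60 sham.

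- Pooled risk 11/120 = 0.0917; z = 0.0833/√(0.0917 × 0.9083 × 2/60) = 1.58; P = 0.11.
- Wilson limits: active 0.0691 to 0.2417; sham 0.0171 to 0.1370.
- Newcombe lower limit: 0.0833 − √[(0.1333−0.0691)² + (0.1370−0.0500)²] = −0.025.
- Newcombe upper limit: 0.0833 + √[(0.2417−0.1333)² + (0.0500−0.0171)²] = 0.197.

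The test reports no significant difference. The interval, −2.5 to +19.7 percentage points, shows that an excess of nearly 20 points is not ruled out. For 6/60 vs 3/60, P = 0.30 and the interval is −5.2 to +15.7 points.

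**Step 5: zero events.** With 0/60, the upper end of the exact two-sided 95% interval is 1 − 0.025^(1/60) = 6.0%; the one-sided 95% bound is 1 − 0.05^(1/60) = 4.9%.

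**The case against.** The strongest reply is that intervals for AE tables are ordinary statistical analysis plan content, that naming tests in a protocol does not forbid them, and that low power for harm is common in trials sized for efficacy. The first two parts stand this far: absence of an interval would not alone be a finding. But 9.4 is not silent. It fixes a test and a threshold as the between-group safety method, and a later plan that follows it inherits that method. The third part stands as a description of practice; it is a reason to estimate, and no support for relying on a test.

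Three stronger readings are tempting, and the protocol does not support them.

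- A reader might infer that harm is judged by P-values alone with no risk estimate at all. Counts and percentages are planned and, reported by arm, give each arm's observed risk. AEs are recorded individually with outcome and relationship to the trial (8.2), and there is a severity scale (8.1.2). What is missing is a between-group estimate with its uncertainty.
- A reader might join 9.4 to the safety presumption in 9.6 and conclude that non-significance will be reported as safety. No section says so. Section 9.6 gives an advance reason for having no monitoring committee and sets no rule for interpreting results.
- A reader might conclude that any real increase in AEs would usually be missed. That depends on its size: 10% vs 30% is detected about 80% of the time and 5% vs 25% about 90%.

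The reply is also right that simply confining P<0.05 to efficacy would not work. MACE is listed under efficacy (7.1) and tested in 9.3.2, so it would be left with a bare P-value. Echocardiography and NT-proBNP are both efficacy measures (2.2.2, 7.1) and safety measures (7.2.2).

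**Conclusion.** The point holds in this limited form. The only between-group safety comparison that 9.4 states is a two-sided P<0.05 test, and 9.3.2 does the same for MACE. At 60 per arm that test misses a doubling of event risk 67% to 98% of the time for assumed sham risks of 10% down to 1%, and slightly more often at 54 per arm. It is adequate for large increases, and for a 0.5-SD shift in a continuous measure it misses 22%. All event rates are assumptions, since the protocol says only that incidence is low; the size of the problem moves with them.

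The conclusion does not depend on the sponsor misreading a non-significant result. Even read correctly, the planned between-group comparison does not tell readers how much harm the data leave open. The efficacy conclusion on depression is unaffected.

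**What to change.** In 9.4, and for MACE in 9.3.2, make estimation the between-group safety comparison:

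- For any AE, any SAE, each AE type and MACE: number and percentage by arm, and the risk difference (active minus sham) with a Newcombe 95% CI. Add the exact limit for an arm with zero events.
- For continuous safety measures: the mean difference with a 95% CI. Include echocardiography and NT-proBNP, stating that they also serve as efficacy measures.
- Add: any P-values for these comparisons are supplementary, and P>0.05 will not be read as evidence that taVNS is safe.

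The cost is a few sentences and a few more lines of output, with no extra patients, visits or data. The downside is a less favourable safety statement, because the intervals will be wide at this sample size.

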2.1 Study Aims

Aim 1: To compare the improvement in depression, anxiety, and quality of life between patients receiving transcutaneous auricular vagus nerve stimulation or sham stimulation using a randomized controlled design.

Aim 2: To compare the improvement in multiple physiological indicators between patients receiving transcutaneous auricular vagus nerve stimulation or sham stimulation using a randomized controlled design.

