6.2 Concomitant Treatment and Follow-up Visits

All enrolled patients will receive standard post-PCI medication and strict secondary prevention for coronary artery disease.

Follow-up visits will occur at 4, 8, 12, and 16 weeks post-randomization. Follow-up content includes: HAMA, HAMD, BDI, GAD-7, PCL-C, and SF-36 scale assessments; HRV measurement; echocardiography; venous blood tests; assessment of smoking/alcohol cessation and lifestyle improvement; record of follow-up visits (time, location, results); presence of angina or heart failure-related symptoms; occurrence of MACE (time, management, outcome); adverse reactions.

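### Protocol 9.4 calls every P<0.05 statistically significant across an unranked secondary set that mostly has no stated visit; Aim 2 alone could involve 18 to 72 tests

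*Protocol*

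**What the plan says.** The significance rule is in section 9.4, under a safety heading, but its wording covers every test: "All statistical tests will be two-sided, with a P-value <0.05 considered statistically significant".

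Section 2.2.1 fixes one primary endpoint at one time, HAMD at Week 8, and 9.5 rules out interim analyses. Section 2.2.2 then lists eleven groups of secondary endpoints. The first is worded "Hamilton Anxiety Rating Scale (HAMA) score during follow-up", with no visit named. Remission is defined on the post-treatment score; most of the others carry no time. Section 6.2 states "Follow-up visits will occur at 4, 8, 12, and 16 weeks post-randomization" and has the scales, HRV, echocardiography and blood tests done at follow-up. Treatment lasts 8 weeks (6.1), so these visits fall during treatment, at its end, and twice after it.

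Section 9.3.2 compares the groups on these endpoints with t-tests, non-parametric tests or chi-square tests. It gives no order, adjustment or visit. Section 2.1 makes the physiological measures an aim in their own right: "To compare the improvement in multiple physiological indicators between patients receiving transcutaneous auricular vagus nerve stimulation or sham stimulation".

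**The concern.** If the protocol were merely silent on multiplicity, the matter could be left to an analysis plan that is not shown. Section 9.4 is not silent. It states when a result counts as significant and makes no exception for secondary endpoints, so a later hierarchy or exploratory label would conflict with it.

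Aim 2 is where this matters most. The only primary endpoint, HAMD, belongs to Aim 1. Aim 2 has no lead measure and no set time, so under the rule as written any one of its measures, at any visit, can be declared a significant effect of stimulation. The visits also ask different questions: a difference at Week 4 is a mid-treatment effect, and one at Week 16 is persistence after treatment has ended.

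**Working it through.** The protocol states no number of comparisons and no familywise error rate, so there is no figure of its own to reproduce. The counts below come from its lists.

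**Inputs**
- Two-sided level per test: 0.05 (9.4).
- Post-baseline visits: 4 (6.2).
- HRV, 10 (2.2.2 item 8): SDNN, SDANN, rMSSD, pNN50, TP, HF, LF, VLF, ULF, LF/HF.
- Echocardiography, 3 (item 9): diastolic diameter, systolic diameter, LVEF.
- Blood, 5 (item 10): NT-proBNP, IL-1, IL-6, TNF-α, hs-CRP.
- Reading of Aim 2: its physiological indicators are taken to be these three groups.

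**Count for Aim 2**
- One visit: 10 + 3 + 5 = 18 tests.
- All four visits: 18 × 4 = 72 tests.
- The table in 10.1 lists 8 HRV items, without pNN50 and LF/HF. On that list the four-visit count is (8 + 3 + 5) × 4 = 64.

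**If stimulation affects none of these measures**

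Expected false positives = m × 0.05, whatever the correlation. The chance of at least one, if the tests are independent, is 1 − 0.95^m.

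| Tests m | Expected false positives | Chance of at least one, independent |
|---|---|---|
| 18 | 18 × 0.05 = 0.9 | 1 − 0.95^18 = 0.603 |
| 64 | 64 × 0.05 = 3.2 | 1 − 0.95^64 = 0.962 |
| 72 | 72 × 0.05 = 3.6 | 1 − 0.95^72 = 0.975 |

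**Allowing for correlation**

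HRV indices come from one recording, and the visits are repeats in the same patients, so independence is an upper case here. The protocol gives no correlations. The values below are assumptions, applied to simulated normal test statistics under the complete null (20,000 to 30,000 runs).

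| Assumed structure | One visit | Four visits |
|---|---|---|
| Endpoints r = 0.3; visits r = 0.5 | 0.51 | 0.91 |
| Endpoints r = 0.5; visits r = 0.5 | 0.40 | 0.81 |
| Endpoints r = 0.7; visits r = 0.7 | 0.28 | 0.57 |
| Separate HRV, echo and blood blocks, HRV and echo r = 0.5 to 0.8; visits r = 0.5 or 0.7 | 0.38 to 0.51 | 0.72 to 0.91 |

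The lowest value, 0.28, is more than five times 0.05 (5 × 0.05 = 0.25).

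**Is fixing the visit enough?** No. At one visit without adjustment the chance is still 0.603 under independence. Holding it near 0.05 would need 0.05/18 = 0.0028 per test at one visit, or 0.05/72 = 0.00069 over four. Under independence each gives about 0.049.

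**The case against.** Four arguments stand against the point.

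- **Multiplicity rules and visits for secondary endpoints are usually settled in the analysis plan.** This holds for what the protocol leaves unsaid. It does not remove a rule that 9.4 states for all tests.
- **The sentence is a general convention.** It does not say that a single secondary P<0.05 will be taken as proof. That is fair, and how results will be reported cannot be known from the protocol. But nothing in the protocol limits the convention.
- **The primary conclusion is untouched.** This stands in full. There is one endpoint, one time and no interim look, so secondary testing cannot inflate its error.
- **The number of tests is inferred.** This also stands. Section 6.2 lists what is collected, and 9.3.2 does not say that each measure is tested at each visit. Hence 72 is an upper count, and 18 is the count at a single visit.

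A reader might go further, count every secondary comparison, reach 129, and conclude that Aim 2 is almost sure to yield a false positive. The documents do not support that. The 129 is (4 scales + 8 SF-36 domains + 18 physiological measures + response + remission) × 4 + MACE = 32 × 4 + 1. It spans both aims, and 129 − 72 = 57 of the tests say nothing about Aim 2. It also assumes that SF-36 is tested by domain, whereas 9.3.2 speaks only of scores; one score gives 25 × 4 + 1 = 101, and a single visit with the domains gives 32 + 1 = 33. It places remission at Week 4 although remission is defined post-treatment. Almost sure would further require near-independence and testing at every visit.

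**Conclusion.** The point holds in a limited form. Section 9.4 labels every P<0.05 significant, while the secondary endpoints are unranked, are not called exploratory, and mostly lack an analysis visit. For Aim 2 this means 18 to 72 tests and 0.9 to 3.6 expected false positives if stimulation affects none of the measures. The chance of at least one is 60% to 97.5% under independence. Under the assumed correlations it is about 28–51% at one visit and 57–91% over four. A false Aim 2 claim is therefore a substantial risk at one visit and more likely than not if all four are tested, but it is not a near certainty.

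These figures rest on the complete null for the Aim 2 measures, on reading its indicators as HRV, echocardiography and blood markers, and on correlations that the protocol does not supply. The Week 8 HAMD test is not affected. The amendment is worth making, but the trial's main conclusion does not depend on it.

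**What to change.** Amend 9.4 so that the label of statistical significance applies only to the Week 8 HAMD comparison. Report secondary endpoints as estimates with 95% confidence intervals and without significance claims.

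Before unblinding, state that Week 8, the end of treatment, is the main comparison time for the scales and physiological measures, and that the other visits are descriptive. Name one lead indicator for Aim 2. A measure that 2.2.2 already describes as parasympathetic or vagal, such as rMSSD or HF, would be a natural choice, but this is a suggestion and not a correction. If a formal Aim 2 claim is wanted, a stated hierarchy or adjustment would also serve.

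Keep MACE as cumulative incidence through Week 16. Section 6.2 records it through that visit, and a uniform Week 8 cut would discard half the follow-up of what is likely to be a sparse event.

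The cost is one paragraph, with no added patients or visits. The downside is that fewer secondary results can be labelled significant.
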